2.1 Purpose

The purpose of this document is to define the study protocol for a remote based summative study to evaluate the IFU used with the LFD Covid-19 virus test kit.

2.2 Objective

The primary objective of this study is to validate that the LFD kit is safe and effective to use by the intended user population in the intended use environment.

2.3 Scope

The following components of the pack user interface will be tested.

1. The LFD test kit and IFU.

The outer packaging and general information presented on the packaging will not form part of this study

2.4 Background

The LFD in-home test kit is currently being developed for distribution to the general public within the United Kingdom.

A key feature in the successful undertaking of the test is the ability for users to understand the steps of use and to understand the general information contained within the IFU.

The DHSC would therefore like to determine whether the IFU design enables safe and accurate test results to be achieved.

2.5 Intended use

The LFD in-home test kit is intended to be used as a self-test by adults and adolescents and performed by adults on children and other adults.

2.6 Intended users

The intended users of the LFD kit are members of the general public. A self-test is expected to be performed from the age of 12. Tests on children below the age of 12 will be undertaken by an adult. Adult caregivers will also undertake the test on other adults who are unable to perform the test on themselves.

Intended User Groups	Experience
Adolescents (aged 12-17 years old)	Naive users to self-administer the test
Adults (aged 18 years old and above)	Naive users to self-administer the test
Adult caregivers for children	Naive users to administer the test on family members below the age of 12
Adult caregivers for adult dependants	Naive adult users to administer the test to other adults who are unable to self-test

Table 1 - Intended user groups

2.7 Study sponsor

The sponsor for this study is the DHSC.

2.8 Intended use environment

The LFD in-home test kit is intended to be used primarily in-home where standard lighting, room temperature, and noise levels are expected.

2.9 User interface

The user interfaces evaluated as part of this summative study will include the following components in Table 2.

Table 2 - Intended user interface

Component	Image	Description	Quantity provided per participant
IFU	<page-header><image/><section-header><section-header><image/><image/></section-header></section-header></page-header>	A paper booklet describing user step to undertake a Covid-19 test	1
Swab inside sealed wrapper		Swab used to take test sample	1
Extraction buffer sachet		Test reagent container	1

Component	Image	Description	Quantity provided per participant
Nozzle cap		Cap placed on extraction tube to deliver reagent drops on test strip	1
Extraction tube		Tube to hold reagent to extract sample from swab	1
Test strip		Test strip to analyse and display test results	1
Bag		Plastic bag to transport and to place items before disposal	1

3 Study design

3.1 Approach

The study will involve 60 participants divided into 4 distinct user groups as described in section 3.6 and following the recruitment selection criteria Appendix 3.

The session will be run in participants homes, using a remote based usability testing platform due to the current COVID-19 pandemic and to be in keeping with the intended use environment.

Participants will be interviewed by an experienced Human Factors session moderator. The session will also be observed by a note taker. The participant and moderator will be linked visually and by audio. The notetaker will have visual or audio access with the participant and moderator. In addition, the note taker and observers will have contact with the moderator using the text chat function.

The participant will be guided in the sequence of locating and using the study material by the moderator.

3.2 Simulated use session

Each study session will be conducted as a 1:1 interview (moderator to participant). Each session will last approximately 60 minutes. The session will be conducted remotely using the remote user testing platform, Validately.

The simulated use evaluation will be conducted with an adolescent user group, adult participant user group, an adult plus child participant user group and a caregiver and adult user group.

The simulated-use test session will require participants to demonstrate the preparation, testing and recording of results using the LFD test kit and IFU. Their performance will be assessed through performance-based measures, knowledge-based questions, root cause analysis and subjective feedback.

3.3 Use environment

Due to the current social distancing measures in the UK, testing will be done remotely. Participants will participate from their own homes and will be advised of the required set up needed. This will include access to a table, chair, hand mirror, torch, cup, tissues and bin.

The use environment will be typical of the environment when patients access and take their LFD test at home.

3.4 Study personnel and general description of roles

Study personnel and description of their roles in Table 3

Role	Description
Study Moderator	Introducing the participants to the session.
woderator	 Ensuring that participants understand the verbal task instruction.
	 Observing the participants performance throughout the simulated use, identifying whether they have committed any use problems.
	 Conducting the pre-task and post-test interview.
	 Video recording of the study to capture participants' interactions with the study items
	 Requesting participants to adjust the webcam as needed, ensuring all interactions with the study items
	 Excluding participants from the study if needed, in accordance with the established exclusion criteria.

Table 3 - Study personnel and roles

Role	Description	
Study	 Recording use errors, close calls, and use difficulties in addition to key	
Observer	findings and participant-reported root causes	

3.6 Participants

The total sample size for this study will be 60 participants administering the test. There will be 4 user groups. A breakdown of composition of each group is detailed Table 4.

Table 4 - Study sample

User groups	Sample size
Adolescents between the age of 12 and 17	15
Adults aged 18+	15
Adults administering the test to an adult dependant	15 caregivers plus 15 dependants
Adults administering the test to a child under the age of 12	15 parents plus 15 children

3.7 Screening criteria

Participants will be screened during the recruitment process and will also be asked a set of screening questions at the beginning of the study session (Appendix 3). Any participants not meeting the screening criteria will be excluded from participating in the study session.

3.8 Participant identification

All participants will be assigned a unique identifying code to ensure their anonymity is protected. This identification code will be:

Adolescents: ADO1, ADO2 etc

Adults: ADU1, ADU2 etc

Adult caregiver for children: ADUC1, ADUC2 etc

Adult caregiver for adult dependent: ADUD1, ADUD2 etc

3.9 Study locations

This summative study will be conducted remotely with participants from within the UK, over a 5 day period, during the week of 16 November 2020.

3.10 Study materials/equipment

The primary study articles are listed below in table 5.

Table 5 - Study materials

Study material	Image	Description of study material
IFU	<image/> <text><section-header><image/></section-header></text>	A5 IFU booklet Version 0.9.2
Test kit		LFD test kit

3.11 Supporting equipment

- Webcam (one per participant)
- Bottle of hand sanitiser (one per participant)
- Moderator's discussion guide
- Observer workbook
- Participant information sheet and Informed Consent Form
- Each participant to provide a table, chair, hand mirror, torch , cup, tissues, timer and bin

3.12 Packaging of supplies sent to participants

For this remote study participants will be sent a package of supplies that they will need to participate in the study. The supplies will consist of:

- A sealed envelope marked A containing the LFD test kit components and IFU
- 1 webcam
- Bottle of sanitiser
- An addressed pre-paid return envelope to return the webcam

Personnel who pack the packages will wear gloves to mitigate any risk of contaminating packed items.

3.13 Study plan

Table 6 - Study plan

Stage of session	Objective	Tasks	User Interface tested	Duration
Technical setup	To organise the technical setup before the study begins	Setup camera and positionUnpack materials	N/A	5 mins
Introduction	Introduce participant to session and material to be used	 Check consent Welcome and introduce participants to session Familiarise participant with study material 	N/A	5 mins
Simulated use	To observe the participant's interaction with the test kit and approach to the test	Open pack and perform test	Market ready sample	30 min
Root cause investigation	Understand the root causes of use errors /difficulties/close calls	Employ a line of questioning to investigate use errors /difficulties/close calls which occurred during the simulated use	N/A	10 mins
Improvements	To gather user feedback on how the IFU could be improved	Employ line of questioning to understand improvements	N/A	5 min
Close session	To observe the participant, repack study materials and advise them to dispose of used test kit components	 Repacking of study material 	N/A	5 min
TOTAL TIME OF	SESSION			60 mins

4 Detail procedures description

4.1 Session introduction

Participants will be asked to review and electronically sign the Informed Consent Form (Appendix 4 and 5). The moderator will ask a number of questions about the participant's personal background, included in the discussion guide (Appendix 6). The interview will confirm each individual's eligibility for participation and provide context for the study data. Participants will be made aware of the test material and how they are expected to interact with the material.

4.2 Introduction to test

Participants will be introduced to the Covid-19 test, its purpose and regimen.

4.3 LFD introduction

The participant will be introduced to the test kit

4.4 Simulated use adult and adolescents

Participants will be asked to open the pack and to follow the steps of use presented to them.

The moderator will observe the participant complete the steps of use. To ensure the task is representative of a real-use scenario, the moderator will not interact with the participant during this task and will not offer help to the participant. The moderator will only verbally interject if the participant gives up on the task, or if the moderator foresees a dangerous scenario developing. A list of tasks and their success/use-error criteria are found in the discussion guide Appendix 6 and section 4.1.1

During the simulated use participants are expected to undertake all steps as described in the IFU to perform a self-test using the LFD test kit.

This task begins with all the study components in their unopened form on the table and ends with the participant indicating that they have done everything they would do at home to perform the test.

4.4.1 Adult/Adolescent self-test use: Use Steps

Use Step	Acceptance criteria	
Prepare your test area and check your kit contents		
Clear, clean and dry a flat surface to place the home test kit on.	Participant cleans the surface they are going to put the contents of the test kit onto and dries the surface	
Wash your hands thoroughly for 20 seconds, using soap and warm water, or hand sanitiser.	Participant goes to wash hands or verbalises would wash hands. Note: Also assessed in Knowledge based questions	
Take the test kit out of the foil packaging and place it onto the cleaned flat surface.	Participant unpacks contents of the test kit placing the items onto the cleaned surface.	
Setup your test		
Use Step 1 Carefully twist or snap open the sachet	The user opens the sachet without spilling any of the fluid.	

Table 7 - Adult/adolescent use steps

	The user pours all of the fluid
Use Step 2 Pour all of the fluid from the sachet into the extraction tube.	The user pours all of the fluid from the sachet into the extraction tube, without the two components touching each other.
Use Step 3 Place the filled tube in a cup or container to avoid spilling it while you use the swab	The user places the tube in a cup and does not spill any solution.
Use Step 4 Check the swab in the sealed wrapper in front of you	Note: Observing correct performance of this use step is challenging, therefore this task will be deemed a success if the user inserts the swab at the correct orientation in Use Step 8.
Use step 5 Gently blow your nose into a tissue.	Participant blows nose into a tissue.
Use step 6 Wash and dry your hands again (or use sanitiser if this is available).	Participant washes their hands.
	Participant opens the swab package without using any tools.
Use Step 7 Open the swab package and gently take out the swab.	Participant removes the swab from the packaging without touching the fabric/soft tip of the swab with their hand or any other surface.
Take your swab sample (or child's)	
	Participant opens their mouth wide and places the swab into the back of their mouth without touching any part of their mouth at this stage
Use step 8 Holding the swab between your fingers, open your mouth wide and rub the fabric tip of the swab over both tonsils (or where they would have been). Do this with firm contact 4 times on each side (use a mirror to help you do this). Carefully remove the swab from the back of your throat.	Participant rubs the fabric/soft tip of swab over both tonsils (or where they would be if they have been removed) with at least 4 observable directional movements.
	Participant removes the swab from their throat without touching any part of their mouth at this stage (not touching tongue, teeth, cheeks, gums etc)

Use step 9 Put the same swab gently into one nostril until you feel a slight resistance (about 2.5cm up your nose). Roll the swab firmly around the inside of the nostril, making 10 complete circles.	Participant puts the same swab fabric/soft tip into one nostril about 2.5 cm up nostril. Participant rolls the swab around the circumference of their nostril in full circles at least 10 times. Participant then places the same swab fabric/ soft tip into the other nostril about 2.5 cm up nostril. Participant rolls the swab around the circumference of
	the other nostril in full circles at least 10 times.
Process the swab sample	
Use step 10 Remove the extraction tube from the cup and place the fabric tip of the swab into the extraction tube so it is in the fluid. Press the tip against the edge of the extraction tube with force, while rotating it around the tube for 15 seconds.	Participant places the fabric/soft tip of the swab into the extraction tube. Participant presses the fabric/soft tip of the swab against the side of the extraction tube with force while rotating the swab around the extraction tube for 15 seconds.
Use step 11 Pinch the tube as you remove the swab to make sure that all the fluid is removed from the soft tip of the swab. Place the swab in the plastic waste bag provided.	Participant takes out the swab whilst squeezing the extraction tube and fabric/soft tip of the swab (to squeeze as much fluid out of swab as possible). Participant puts the swab into a plastic bag and disposes of it into their household rubbish.
Use step 12 Press the nozzle cap tightly on to the extraction tube to avoid any leaks	Participant presses the nozzle cap tightly onto the extraction tube (to avoid leaks).
Use step 13 Gently squeeze the extraction tube to place 2 drops of liquid onto the specimen well on the test strip.	Participant tips the extraction tube to place 2 drops of liquid onto the test strip sample well.
Use step 14 Place the test strip on a flat and level surface Check the time or set a timer if you have one. Wait 30 minutes to read your result.	Participant places test strip on a flat surface Participant checks the time or sets timer for 30 minutes and leaves the test strip without touching it. After 30 minutes the participant reads the result.

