4.5 Simulated use caregivers of paediatrics and dependents

Participants will be asked to open the pack and to follow the steps of use presented to them to perform the test on their child/ dependent.

The simulated use steps to be observed are as follows in table 8:

Table 8 - Use	Steps for	adult testing	a child	or dependent

Use Step	Acceptance criteria
Repeat Use Steps 1 through 7 as per Section 4.4.1 (table 7) of this protocol, then proceed with Use Steps 8 and 9 below.	As per section 4.4.1 (table 7)
Use step 8 (child/dependant) Ask the child to open their mouth wide, then rub the fabric tip of the swab over both tonsils (or where they would have been). Do this with firm contact 4 times on each side. Carefully remove the swab. If you cannot swab the tonsils, you can swab both nostrils.	Participant rubs the fabric tip of the swab over both tonsils with firm contact 4 times on each side, without touching any part of the child/ dependent's mouth at this stage (not touching tongue, teeth, cheeks, gums etc). Participant removes the swab from the child/dependent's throat without touching any part of their mouth at this stage (not touching tongue, teeth, cheeks, gums etc)
Use Step 9 (child/dependent) Put the fabric tip of the same swab gently into one of their	Participant puts the fabric tip of the same swab gently into one of their nostrils Participant rolls the swab firmly
nostrils until you feel some resistance. Roll the swab firmly around the inside of the nostril, making 10 complete circles and slowly remove it. If you could not swab	around the inside of the nostril, making 10 complete circles and slowly removes it.
their throat repeat in their other nostril.	If the user could not swab the throat, they repeat in the other nostril.
Repeat Use Steps 10 through 14 , as per Section 4.4.1 (table 7) of this protocol.	As per section 4.4.1 (table 7)

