4.11 Analyses

After all sessions are completed, the collected data will be analysed to determine if the task performance was a success, use error, close call, or use difficulty, as per the criteria defined in Table 10. Root cause analysis will be conducted on all tasks where use errors, close calls, and use difficulties were present. This analysis will draw upon study video data, participant responses from post-task interviews, and expert review of the use problem.

Outcome	Definition	Root Cause Investigation Required?	Method of Scoring Data
Success	Participant performs the task correctly on the initial attempt without assistance	No	Success Close Call Use Error N/A

Table	10 -	Scoring	definitions
-------	------	---------	-------------

Outcome	Definition	Root Cause Investigation Required?	Method of Scoring Data
Close Call	 Any instance in which a participant makes a use error e.g. by attempting to undertake an action without accurate reference to the IFU, but then retries resulting in a successful completion of a user step. This outcome also considers: The user verbally expresses frustration or facial expressions and body postures indicate frustration when using the device; The user re-reads the same section of the IFU during a task, in an attempt to comprehend a sequence of steps use The user is able to accomplish a task or step, but experiences frustration or discomfort in the process of doing so. 	Yes	Success Close Call Use Error N/A
Use Error	 Any action or lack of action while using the packaging that leads to a different result than that intended by the manufacturer or expected by the user, including: A participant's inability to complete a task; A deviation from the IFU that leads to a device response that is different than intended or expected by the participant; An instance where the participant requires assistance from study personnel to advance through tasks. The following will not be considered use errors: A malfunction of the packaging that causes an unexpected result. 	Yes	Success Close Call Use Error N/A

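### The self-test acceptance criterion for tonsil swabbing (Table 7, Use step 8) omits the per-side count and the firmness that its own step text, the scoring sheet and Table 8 all state

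*Protocol*

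**What the plan says.** Four places in the protocol bear on how Use step 8, the throat swab, is scored in people testing themselves.

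- **Section 4.4.1, Table 7, step text:** "Do this with firm contact 4 times on each side (use a mirror to help you do this").
- **Section 4.4.1, Table 7, acceptance criterion in the same row:** the participant rubs the tip over both tonsils "with at least 4 observable directional movements".
- **Section 6.3.1, self-test scoring sheet in the discussion guide:** the first column, headed as holding both the use step and the acceptance criteria, repeats the step text with its count per side. The minimum from the Table 7 criterion does not appear.
- **Section 4.5, Table 8, caregiver criterion for the corresponding step:** "Participant rubs the fabric tip of the swab over both tonsils with firm contact 4 times on each side". The caregiver scoring sheet (section 6.4) has the same count.

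Section 4.4 does not rank these sources: "A list of tasks and their success/use-error criteria are found in the discussion guide Appendix 6 and section 4.1.1". There is no section 4.1.1 in the protocol; the table stands in 4.4.1, and the discussion guide is printed as Appendix 10. In section 4.11, Table 10 defines Success as "Participant performs the task correctly on the initial attempt without assistance" and requires no root cause investigation for it.

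**The concern.** The acceptance criterion turns what is seen on video into an outcome. Here it is looser, on its face, than the instruction it is meant to test. A self-tester who makes two movements on each tonsil has not done what the instructions ask, yet satisfies the Table 7 criterion as worded. A scorer working from the sheet would not pass the same session.

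Two things are at stake. First, the step 8 outcome is not reproducible for the self-test groups, because two documents that both claim to hold the criteria give different answers. Second, a participant passed under the looser wording is not followed up unless a use difficulty is noted separately. The study asks whether the instructions lead to safe and accurate results (section 2.4), so a weakness in this instruction could go unexamined at a sample-taking step.

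**Working it through.** **Inputs.** Group sizes are from section 3.6, Table 4: 15 adolescents, 15 adults, 15 caregivers of adult dependants and 15 parents. The total is 4 × 15 = 60, which reproduces the stated sample size. The protocol gives no power calculation, and the point needs none. The self-test groups are 15 + 15 = 30, so the Table 7 criterion for step 8 applies to 30/60 = 50% of participants.

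**Movement count.**
- Step text, both scoring sheets and Table 8: 4 per side × 2 sides = 8.
- Table 7 criterion read literally: at least 4 over both tonsils.
- Ratio: 4/8 = 50% of the instructed count.

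**A test case.** Take two movements on each side, 2 + 2 = 4. Both tonsils are rubbed and four movements are seen, so Table 7 is met. The per-side count is 2 against 4, so neither the sheet nor Table 8 is met. If a back-and-forth stroke counts as two directional movements, two such strokes would be enough and the literal bar is lower still.

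**Is the missing per-side count just loose wording?** The next row of Table 7 suggests not. Its nostril criterion sets the count for one nostril and then again for "the other nostril in full circles at least 10 times". The table counts by side where it means to, which supports the literal reading of the tonsil line without proving it. Table 7 also states openly when a criterion has been relaxed because a step is hard to observe (Use step 4). It says nothing of the kind at step 8.

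**Firmness.** The step text, the sheets and Table 8 ask for firm contact. The Table 7 criterion asks for rubbing, which is contact, but not for firm contact.

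**How many participants could be affected.** No figure in the protocol gives the share *q* of self-testers who would make four to seven movements in total, so *q* is an assumption and is varied. The expected number is 30 × *q*, and the chance of at least one is 1 − (1 − *q*)^30.

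| Assumed *q* | Expected of 30 | Chance of at least one |
|---|---|---|
| 5% | 1.5 | 0.785 |
| 10% | 3 | 0.958 |
| 20% | 6 | 0.999 |
| 30% | 9 | >0.999 |

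These are participants who would meet the literal Table 7 criterion and fail a per-side rule. An uneven split of eight or more movements, such as 6 + 2, would also pass one and fail the other, and is not counted here.

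**The case against.** The strongest reply is that the conflict may never reach the data. Table 7 does not say that the four movements are a total, and with the per-side instruction beside it a scorer could read four per tonsil. The form on which outcomes are ticked already carries the per-side count for all four groups. Every session is recorded (section 4.10), and outcomes are determined from the data after all sessions (section 4.11), so step 8 could be rescored wherever the footage shows it.

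Much of this stands, and it limits the claim. It does not remove the contradiction: the protocol names both the sheet and its own table as sources of the criteria and says nowhere which prevails. Rescoring also helps only in part. Participants are questioned about root causes during the session (section 4.7), so someone passed at the time may not have been asked, which leaves video and expert review alone.

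A reader might infer more: that half-done swabbing is a Success in two groups and a Use Error in the other two, so that step 8 rates cannot be pooled. The documents do not support this.
- The first half requires Table 7 to override the sheet, which is not stated.
- The second half is an inference. Table 10 defines a Use Error as "Any action or lack of action while using the packaging that leads to a different result than that intended by the manufacturer", with the user's own expectation as an alternative, and an error followed by a successful retry is a Close Call. The caregiver step also provides for swabbing both nostrils when the tonsils cannot be swabbed.
- Section 4.11 plans classification by task and root cause analysis. It states no pooled step 8 rate and no comparison between groups.

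**Conclusion.** The contradiction is real and in current text. The Table 7 criterion for Use step 8 leaves out the count per side and the firmness that its own instruction, the self-test scoring sheet and Table 8 include. On a literal reading it accepts 4 movements where 8 are instructed. Up to 30 of the 60 participants are exposed to an outcome that depends on the source used.

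The number actually misclassified cannot be derived from the protocol. The range of 1.5 to 9 of 30 rests on an assumed 5% to 30% of self-testers making four to seven movements, and on the scorer applying Table 7 literally. If scorers use only the sheet, or read four per tonsil, the number is zero for the count, though the wording remains in conflict. Nothing here bears on which swabbing count is clinically right.

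**What to change.** Before the first session, reconcile five texts to one stated rule on the count per side and on firmness: the Table 7 step text, the Table 7 criterion, the Table 8 criterion and the two scoring sheets (sections 6.3.1 and 6.4). The sponsor decides which count stands. State whether a back-and-forth stroke is one movement or two, and correct the cross-reference in section 4.4 so that scorers know where the governing criteria are.

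Score step 8 in all four groups under that rule. Have the observer count movements per side from the planned video where they are visible, and record where they are not.

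The editing cost is small: chiefly one criterion line in Table 7, if the per-side rule is kept, since the sheets already carry it. If another rule is chosen, the step text, Table 8 and the sheets change too. Counting by side adds some review time. The downside is that reported step 8 success in the self-test groups may fall. The timing matters because fieldwork lasts five days (section 3.9), and a rule settled afterwards would be chosen with the sessions already seen.
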